6. PARTICIPANTS

In selecting participants, Investigator shall carefully examine whether or not it is appropriate to ask for participation in the study, paying attention to matters including dependence on the principal investigator or other personnel, from the perspective of protection of human rights.

Among patients who have “Target Disease,” those who meet “Inclusion Criteria” and do not meet any of “Exclusion Criteria” will be examined.

6.1 Target Populations

Participants who were diagnosed with acute musculoskeletal pain will be recruited in this study.

The acute musculoskeletal pain caused by arthritis such as osteoarthritis (OA) with Grade 0 until III Kellgren-Lawrence (KL) grading, or musculoskeletal disorders such as ankle sprain, patella tendinitis, tennis elbow, and back pain as mentioned in topical NSAIDs indication that approved by BPOM RI.

Diagnosis criteria were made by history taking, physical examination and radiologic evaluation if necessary.

Justification:

Acute musculoskeletal pain is defined as pain arising from the musculoskeletal system (muscles, bones, joints, ligaments, and tendons) that is sudden in onset and relatively short-lived.

- Subject with musculoskeletal pain caused by Osteoarthritis, Grade 0 – Grade III Kellgren-Lawrence
 - Grade 0 : No radiographic evidence of osteoarthritis.
 - Grade 1 (Doubtful) : Possible osteophytes (bone spurs) and doubtful joint space narrowing.
 - Grade 2 (Minimal) : Definite osteophytes and possible joint space narrowing.
 - Grade 3 (Moderate) : Moderate joint space narrowing, multiple osteophytes, some sclerosis (increased bone density), and possible bone deformity.
- Subject with musculoskeletal pain caused by musculoskeletal disorder, such as :
 - Ankle sprain is a common injury that occurs when the ligaments in the ankle are stretched or torn due to a sudden twisting or rolling motion of the foot.
 - Patellar tendinitis, also known as jumper's knee, is an inflammation of the patellar tendon, which connects the kneecap (patella) to the shinbone (tibia).
 - Tennis elbow, also known as lateral epicondylitis, is a condition characterized by pain on the outer side of the elbow, specifically near the bony prominence (lateral epicondyle). It's typically caused by overuse or repetitive motions of the forearm muscles, which can lead to tiny tears and inflammation in the tendons that attach these muscles to the elbow.
 - Back pain, also known as dorsalgia, refers to pain experienced in the back, from the base of the neck to the top of the buttocks.

6.2 Inclusion criteria

- Outpatient in a health care setting.
- Between the ages of 18 - 60 years of either sex.
- Patients diagnosed with musculoskeletal pain as described in the target population.
- Patient can read and understand how to fill out the assessment form and diary.
- Patients gave written consent to participate in the study independently.

6.3 Exclusion criteria

- Patient who has osteoarthritis with Grade IV Kellgren-Lawrence (KL) grading.
- Patients who underwent any of the following treatments:
 - Paracentesis and drainage of joint

- Intraarticular injection (joint protection agents, local anesthetic, etc.)
- Nerve block (including trigger points)
- Patients are being treated with an analgesic opioids for their musculoskeletal pain.
- Patients being treated with anti coagulant therapy such as warfarin, clopidogrel.
- Patients being treated with oral corticosteroids 3 days before and until signed the informed consent.
- Patients being treated using rigid orthoses those requiring such treatment
- Patients with neuropsychiatric disorders including depression, dementia, schizophrenia, and anxiety neurosis
- Patients with Grade 3 hypertension (systolic blood pressure ≥ 180 mmHg and diastolic blood pressure ≥ 110 mmHg regardless of the use of an antihypertensive drugs)
- Patients with acute peptic ulcer
- Patients with bronchial asthma or those with current or previous aspirin-induced asthma (asthmatic attacks induced by NSAIDs and other relevant drugs)
- Patients with a history of hypersensitivity or allergy to NSAIDs
- Patients with serious hepatic disease, renal disease, cardiac disease, hematologic disease, or malignancy
- Patients with a history of dermatitis requiring treatment with topical agents
- Patients with dermatitis or wounds at the application site of the study drug
- Pregnant women, women who may be pregnant, women who wish to become pregnant during the study, or nursing women
- Patients considered by the Investigator to be inappropriate as participants of this study

6.4 Withdrawal Criteria

- Any clinical adverse event, serious illness, or other medical condition identified by the investigator or treating doctor that suggests continued participation is not in the subject's best interest.
- A voluntary decision by the patient to withdraw from the study.
- If the subject was found to have entered the study in violation of the protocol or if the patient was uncooperative during the study.
- Any subject who required the use of an unacceptable concomitant medication—defined as a medication that interfered with the study—will be addressed with justification from the investigator.

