5. STUDY DESIGN

This is a Phase 3, Randomized Control Trial, Multi centre, Single-blind, and Parallel group of 6 ± 1 days duration of data collection after topical application to compare the efficacy and safety of standard treatment of musculoskeletal pain in adult populations.

Justification :

- Phase 3 (Confirmatory study)
The study is conducted to demonstrate whether or not a product offers a treatment benefit to adult participants with musculoskeletal pain between test drug (Piroxicam plus Counterirritant) and commonly used NSAID topical products, Piroxicam gel, Diclofenac gel
- Randomized Control Trial (RCT)
Participants are randomly assigned to different treatment or control groups to minimize bias and allow for causal inference.
- Multi centre
The study will be conducted in 2 sites
- Single-blind
To keep this study maintain the integrity of the data, the investigational product will be given a white sticker to cover all over the tube of investigational products. On top of the tube, there is a study label with unique code to differentiate the test drug and comparator drug. With this procedure, participants will not know which products that assigned to them. Therefore participants can be blinded.
- Parallel

The study in which two groups of participants receive Piroxicam plus Counterirritant gel or Piroxicam gel, or Diclofenac gel. Participants are assigned to one of the treatment arms at the beginning of the trial and continue in that arm throughout the length of the trial. Assignment to a group usually is randomized.

5.1 Primary End-Point:

The primary end-point is the difference of musculoskeletal pain reduction ≥ 3 scores, of the response to treatment that can be seen through Brief Pain Inventory (BPI) scores.

Justification:

- The Brief Pain Inventory (BPI) scores.

It is a medical questionnaire that is used to assess pain. It has also been validated for pain assessment chronicle. There are 9 questions related to the pain experienced by the participants. The pain assessment will be given in the form of a score, namely a score of 0 - 10.

Score 0 : No Pain

Score 1 – 3 : Mild Pain

Score 4 – 6 : Moderate Pain

Score 7 – 10 : Severe Pain

The difference BPI scale ≥ 3 , from initial scale of pain to the end of treatment will be captured as the primary efficacy endpoint.

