6.9 Study Drugs Labelling

A label is needed for the study drug used.

Investigational products will be given to Participants in tube only, no individual box.

All Investigational Products tubes will be covered by white sticker, leaving only the tip of the tube containing the batch number and expiration date information. On top of the white sticker will be a study drug label that have specific code and number.

Below is the labelling process for investigational products :

The packaging label from investigational products will be covered by a white secured sticker. Only the bottom side (tail) which contains the batch number information is left open.

Clinical study label will be put on the top of white sticker.

PRODUK INVESTIGASIONAL NO. BATCH : 4M3101 TGL KADALUARSA : Dec 27 NO. REG : DTL1124403528A1 PENYIMPANAN : Simpan dibawah suhu 30° C <small>Dibuat oleh : PT. Taisho Pharmaceutical Indonesia, Tbk</small>	NO. OBAT : C001 NAMA SITE : Klinik Utama Eminence
PRODUK INVESTIGASIONAL NO. BATCH : 4M3101 TGL KADALUARSA : Dec 27 NO. REG : DTL1124403528A1 PENYIMPANAN : Simpan dibawah suhu 30° C <small>Dibuat oleh : PT. Taisho Pharmaceutical Indonesia, Tbk</small>	NO. OBAT : C199 NAMA SITE : St. Carolus Sports Clinic by Eminence

Final label on the tube

Every tube will be numbered with drug number sequentially, as detailed:

Test drug (Yellow sticker)	Comparator drug (Orange Sticker)	Comparator drug (Brown Sticker)
C001	H001	P001
C002	H002	P002
C003	H003	P003
etc. until the last of stock	etc. until the last of stock	etc. until the last of stock

- Initial “C” for study drug and 3 digits number
- Initial “H” for comparator drug and 3 digits number
- Initial “P” for comparator drug and 3 digits number

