6.12 Dispensing, Storage, Management, and Collection Procedures

The Study Drug Handling Manual will be provided and completed to ensure the study drugs are prepared, shipped, stored, dispensed, and returned to comply with regulations.

The Investigational Products will be relabelled in Sponsor Technical Operations Plant Site. After the Sponsor ensures the quality of the product, the study drug will be relabeled, which means that this drug is used explicitly for clinical studies.

The sponsor will deliver the study drug from the Technical Operations plant to each research site by courier, where it can monitor the temperature of the study drug delivery below 30°C.

The Study Coordinator from each research site will ensure the storage of study drugs.

During the study, the distribution of study drug participants will be prescribed by the Investigator based on randomization and dispensed to the participants by the Sports Therapist during the recovery program.

Use GraphPad QuickCalcs (<https://www.graphpad.com/quickcalcs/randomize1/>) to generate a random allocation list, ensuring equal numbers for each treatment group:

- Group A: Piroxicam + Counterirritant
- Group B: Piroxicam
- Group C: Diclofenac

Each eligible participant will be assigned a unique subject ID upon enrollment. The study coordinator will match the subject ID to a treatment group based on the pre-generated list. All tubes will be labeled with a sticker displaying only the randomization code to maintain blinding of both participants and investigators. The tube will then be dispensed to the participant according to the assigned code. Only the investigator will have access to the full randomization list.

At the end of the study period, all study drugs will be returned by the participants to each site. This return process will be assisted by each Study Coordinator. An then be sent to Technical Operations for destruction.

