6.14 Unacceptable Concomitant Medication

As explained in the clinical data and pharmacokinetics and pharmacodynamics of Paracetamol, the drugs mentioned below are known to have interactions with Paracetamol. For this reason, it is not acceptable to get the following treatment:

- Opioid Analgesics
- Oral Non Steroid Anti Inflammation Drugs
Caution is recommended when analgesic products are used in combination because of possible increases in adverse events (e.g. nephrotoxicity, gastrointestinal lesions, bleeding).
- Alcohol
- Anticoagulants – Oral, Injection: Piroxicam is highly protein bound. There is therefore a possibility of interaction with such drugs as coumarin anticoagulants

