7.10 STATISTICAL ANALYSIS

7.4.1 Analysis Sets

In the efficacy analysis, the **Per Protocol Set (PPS)** will be used as the primary analysis set, while the **Full Analysis Set (FAS)** will serve as the secondary analysis set. For safety analysis, the **Safety Analysis Set** will be used. The definitions are as follows:

- **Per Protocol Set (PPS):**
The PPS includes participants who do not have any major protocol violations (such as not meeting inclusion/exclusion criteria or poor compliance), and who have completed the required assessments of the primary endpoint as specified in the protocol.
- **Full Analysis Set (FAS):**
The FAS includes all participants who received at least one dose of the study drug and had at least one post-baseline assessment for efficacy endpoints. This set reflects the intention-to-treat principle.
- **Safety Analysis Set:**
The Safety Analysis Set includes all participants who received at least one dose of the study drug and had at least one post-baseline safety assessment. All safety data, including adverse events and rescue medication use, will be analyzed in this set.

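### Use of an unacceptable medication is handled case by case by an investigator who may know the arm, so the primary Per Protocol Set can lose participants unequally between arms

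*Protocol*

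**What the plan says.** - **Consequence of a barred drug.** Section 6.4 of the Protocol lists this situation among the withdrawal criteria: "unacceptable concomitant medication—defined as a medication that interfered with the study—will be addressed with justification from the investigator". It does not say whether the participant is withdrawn, kept, or excluded from any analysis.
- **Which drugs.** Section 6.14 names opioids, oral NSAIDs, alcohol and anticoagulants, introduced by "it is not acceptable to get the following treatment". It gives no consequence for the participant or for the analysis.
- **Who knows the arm.** Section 6.12 states: "Only the investigator will have access to the full randomization list". The same paragraph says that the tube labels serve "to maintain blinding of both participants and investigators". Section 5 calls the trial single-blind and describes blinding of participants only: "participants will not know which products that assigned to them". Section 6.9 numbers the tubes with a different letter (C, H or P) and a different sticker colour for each product.
- **Who sees the outcome.** Under 7.7.2 the Day 0 examinations, including the participant's pain form and the doctor's pain forms, are repeated at the later visits.
- **The primary set.** Section 7.4.1 makes the PPS primary for efficacy: "The PPS includes participants who do not have any major protocol violations". Its examples are eligibility failures and poor compliance. Barred medication is not named. Membership also requires completed primary-endpoint assessments. The FAS is the secondary set, and the sensitivity analysis under Missing Data Handling.

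**The concern.** The Protocol has a list of barred drugs but does not tie a uniform consequence to it. The consequence is left to individual judgement, under a description (interference with the study) that can only be applied after the event. That judgement belongs to a person who, on one explicit statement, holds the allocation list and who also follows each participant's pain. Two participants who took the same oral NSAID could be handled differently, and nothing in the text requires otherwise.

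This matters because the objective is equivalence within ±1.0 point and the PPS carries the primary conclusion. If participants doing badly are dropped more readily from the worse arm than from the other, the two means move together. The error that an equivalence trial must control, declaring equivalence when the true difference is at or beyond the margin, then becomes more likely.

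**Working it through.** **Step 1: the route from 6.4 to the primary set.** Section 6.4 does not mention analysis sets and 7.4.1 gives the investigator no role in assigning them. Two indirect routes remain.

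1. A participant withdrawn under 6.4 before Visit 3 may have no completed primary-endpoint assessment and then fails the PPS completion requirement.
2. Use of the drug may be called a major violation. The examples in 7.4.1 are not exhaustive, so this can be done for one participant and not for another.

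**Step 2: inputs for the size.**

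- Margin 1.0: sections 6.7 and 7.4.2.
- SD 1.81: section 6.7.
- 54 evaluable per arm: section 6.7, and 180 × 0.9 / 3 = 54. The formula printed in 6.7 does not itself give 54: ((2.39 + 0.84) × 1.81 / 1.0)² = 34.2. That is a separate matter. Here 54 serves only as the planned evaluable number.
- Test level: 0.05 (the general level in 7.4.2) and 0.05/3 = 0.0167 (the adjusted level in 6.7). Both are shown, one-sided.
- Assumed, not in the Protocol: normal outcomes; the test gel truly 1.0 point worse; k participants removed from the test arm and none from the comparator; each removed participant 3 points worse than the rest of the arm.

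**Step 3: formula.** If k of 54 participants lie g points below the rest, removing them moves the arm mean by g·k/54. The standard error of the difference is 1.81 × √(2/54) = 0.348. With the true difference at the margin, the chance of false equivalence is about 1 − Φ(z − shift/0.348), where z = 1.645 at 0.05 and 2.128 at 0.0167.

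**Step 4: results for g = 3.**

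| k | Shift | Shift/SE | Formula, 0.05 | Simulated, 0.05 | Formula, 0.0167 | Simulated, 0.0167 |
|---|---|---|---|---|---|---|
| 0 | 0 | 0 | 5.0% | 5.2% | 1.7% | 1.7% |
| 2 | 0.11 | 0.32 | 9.2% | 9.1% | 3.5% | 3.2% |
| 3 | 0.17 | 0.48 | 12.2% | 12.1% | 5.0% | 4.6% |
| 5 | 0.28 | 0.80 | 19.8% | 19.2% | 9.2% | 8.1% |

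The simulated columns are a two one-sided t-test procedure with pooled variance, 20,000 runs. The formula ignores the few lost participants, so it runs slightly high at k = 5.

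**Step 5: how far this depends on the assumptions (one-sided 0.05).**

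- Gap of 1 point instead of 3, k = 2 to 5: about 6 to 8%.
- Three removed from one arm and two from the other, gap 3: net shift 3 × (3 − 2)/54 = 0.056, giving about 7%.
- Equal numbers removed from both arms with the same gap: about 5%, so no inflation.
- Upper bound, the actual worst 1, 3 or 5 outcomes removed from the test arm only: 8.2%, 15.7% and 25.2%.

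**The case against.** A reader might infer that the investigator decides who is in the PPS, knowing arm and outcome. The documents do not say that. Section 6.4 concerns withdrawal, 7.4.1 names nobody to decide membership, and classifying violations in a masked review is commonly left to a statistical analysis plan, which is not shown here. This stands, and limits the point to the two indirect routes. It does not dispose of it: a later masked review cannot recover Visit 3 scores lost through withdrawals already made.

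A reader might also take knowledge of the arm as settled. It is not, because 6.12 also says investigators are blinded. The explicit statement about the list and the arm-specific tube codes sit better with the single-blind design, but the two statements have to be reconciled.

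Nor does 6.4 clearly set the 6.14 list aside. It uses the same term, and its description may be a loose gloss on the list. What stands is that the two wordings differ and neither fixes a consequence.

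There are safeguards. The FAS keeps anyone with one dose and one post-baseline efficacy assessment, so selective PPS removal could show as disagreement between the sets. Section 7.8.2 calls for the scheduled observations at discontinuation and a recorded reason, and 7.11.1 requires deviations to be recorded. These reduce the risk. However, 7.8.2 is tied to the discontinuation criteria, a list separate from 6.4, and an assessment on the day of stopping need not be the Visit 3 endpoint.

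Finally, it is not established that users of barred drugs are those whose gel fails. The list includes alcohol and anticoagulants, paracetamol rescue is supplied, and a barred analgesic would itself lower the recorded score. The 3-point gap is therefore only illustrative.

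**Conclusion.** The point holds as a weakness in what the Protocol fixes. The consequence of barred medication is discretionary, the person exercising the discretion may know the arm and sees the pain course, and the primary set can be affected through early withdrawal or a violation label. It does not show that removals will be selective.

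The size is conditional. With 54 per arm, SD 1.81, the true difference at the margin, and one-sided removal of 2 to 5 participants who are 3 points worse, false equivalence rises from 5% to about 9–19% at one-sided 0.05, and from 1.7% to about 3–8% at 0.0167. Smaller gaps or nearly balanced removals give much less, and equal removals essentially nothing. The FAS analysis can expose a discrepancy, but the conclusion rests on the PPS. The point should be corrected; confidence is medium because the route is indirect.

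**What to change.** - **Section 7.4.1:** define the medication violation, for analysis-set purposes, by the 6.14 list as recorded in the diary and the concomitant-medication log, and apply it identically in all arms. Decide PPS membership for everyone in one review before database lock, from a listing without arm, tube number or BPI scores. State that the investigator's justification is recorded but does not decide the analysis set.
- **Section 6.4:** refer to the 6.14 list so that the two definitions agree, and state that the Visit 3 BPI is still collected where possible after a withdrawal under this section. Without that sentence the withdrawal route stays open.
- **Section 6.12:** reconcile the statement on list access with the statement on investigator blinding.

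Clinical decisions on continuing treatment are unchanged. The cost is a few sentences, one masked listing review and possibly a slightly smaller PPS, since the list is broad; no extra participants are needed. A uniform rule removes the choice but not an imbalance that arises because one arm truly uses more barred medication, so the FAS result still has to be read beside the PPS result.

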6.5 Preparation of Consent Form and Other Written Information for Patients

The principal investigator prepares the consent form and other written information for patients that are used to obtain the consent of participants to participate in the study and revise them as necessary, in cooperation with the sponsor. The principal investigator submits the prepared or revised documents concerned to the sponsor and obtains prior approval of the institutional review board.

6.5.1 Matters That Should be Included in Consent Form and Other Written Information for Patients

The consent form and other written information for patients must include the following matters at least.

- That the study involves research.

- Study objectives
- Names and contacts of the investigators
- Study methods
- Anticipated advantages for physical and mental health of participants resulting from the study drugs (if such advantages are not expected, to that effect) and anticipated disadvantages to participants
- Presence or absence of other therapeutic methods for the patients concerned and the important benefits and risks anticipated in association with these therapeutic methods
- Anticipated duration of participation in the study
- That participation in the study is voluntary and the participants can reject to participate or stop participating in the study any time. That the participants will neither be treated unfairly due to such rejection or withdrawal nor lose the benefits they should have received for the reason of not participating in the study
- That monitors, people in charge of audit, institutional review boards and other personnel and the regulatory agency can view the source documents related to the medical care That subject confidentiality will be protected in such viewing That, by signing the consent form, participants agree to the viewing
- That subject confidentiality will be protected when the study results are published
- Consultation service at the study site participants should make inquires to or contact when they wish to have further information regarding the study and their rights or when any health hazard associated with the study occurs
- Compensation and treatment participants can receive when health hazards associated with the study occur
- Anticipated number of participants participating in the study
- That any information that may influence the intention of participants to continue to participate in the study is promptly provided to participants if such information was obtained
- Conditions or reasons for terminating the participation of certain participants in the study
- Details of the expense of participants, if any
- Details of the payment in cash, etc. to participants, if any
- Rules that participants should follow
- Matters regarding the institutional review boards that investigate and deliberate the adequacy of this study, including the types of institutional review boards, etc. and the matters investigated and deliberated by each institutional review board

